Up to ten subjects with tinnitus who participated in a previous rTMS study (i.e., 109033) and who agreed to be contacted for future studies will be invited to participate. The design of Aim 3 is an, open-label, feasibility study with pre and post assessments. All subject visits will be to the TMS laboratory and the Brain Imaging Research Center (BIRC) of the Psychiatric Research Institute. There will be a total of four study visits to the TMS laboratory, with one visit including a walk to the BIRC for the MRI scan, and three follow-up phone calls, emails or text messages used to obtain tinnitus ratings. The time required for each visit ranges from 1 hour when TMS/EEG is not measured to 3.5 hours when TMS/EEG is measured. During the first visit, subjects will complete the informed consent process and reestablish that they meet inclusion and do not meet the exclusion criteria. They will then complete a baseline TMS/EEG recording and make analogue ratings of tinnitus awareness, loudness and annoyance. An MRI image of the brain may be acquired as part of the first or second visit. During visits 2-4, subjects will be treated with tDCS over the DLFC (2 mA for 20 minutes) prior to receiving rTMS over the TC (1800 pulses delivered at 1 Hz and 110% of motor threshold). Following the treatment during visit four, subjects will have their second TMS/EEG recording. The study endpoints are the same as those in Aims 1 and 2 except that actual ratings of tinnitus are used in place of the procedure for measuring tinnitus like perception in healthy subjects.

Study Population

Aims 1 & 2

Study subjects will be recruited via advertisement. Twenty (20) healthy subjects between the ages of 19-65 years will be recruited. Screening measures include the Transcranial Magnetic Stimulation Adult Safety Screen (TASS).³⁷ A request for medical records either from UAMS or an external service provider may be necessary to ensure that subjects do not meet exclusion criteria.

Inclusion Criteria

- 1) complete the informed consent process
- 2) men and women, age: 19–65 years (a range reflective of our tinnitus samples, (e.g., CLARA IRB# 109639 *PET-CT to target and validate TMS as treatment for Tinnitus*)
- 3) negative pregnancy test (female subjects of childbearing age must take a pregnancy test).

Study Title: Regulating homeostatic plasticity and the physiological response to rTMS
PI: [name]
Institution: University of Arkansas for Medical Sciences

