Methods for TMS targeting. A template MRI scan will be uploaded into the Brainsight frameless stereotaxy system (Rouge Research, Montréal, Québec, Canada) and used to track stimulation delivery for all subjects. Brainsight uses 3D infrared tracking position sensors to reference the MRI to anatomical landmarks on the subject's head and to the TMS coil. Digitized markers can be placed on the MRI in Brainsight to ensure that the TMS coil is placed in the same locations from session to session. Brainsight will be used to target rTMS over the caudal two-thirds of the superior temporal gyrus (BA 22 in TC). During TEP recording, Brainsight will be used to target the TMS coil over BA 22 in the TC and to position the TMS coil over the convexity of the superior frontal gyrus where TEPs from the DLFC will be obtained. All stimulation sites will be marked in the Brainsight Stereotaxic system (RougeResearch) to ensure precise session to session targeting.

Methods for active and sham rTMS and study blinding. The MT will be established at the

Figure 5. Electrode location mock-up.

Study Title: Regulating homeostatic plasticity and the physiological response to rTMS
PI: [name]
Institution: University of Arkansas for Medical Sciences
Support: Department of Neurobiology and Dev. Scs.

beginning of each test session. A technician will set up equipment for each test session while the subject is being prepped for EEG recording, to keep them blind to condition. To check integrity of the blind, subjects will be asked to guess whether they received active or placebo stimulation at the end of each treatment session. Subjects are not providing subjective responses to intervention, which minimizes the possibility of experimenter bias. Persons who process EEG data for analysis and the biostatistician will be kept blind to condition using session codes. These procedures were used successfully in previous studies.⁴⁵

Aim 3.

The methods for tDCS preconditioning in Aim 3 is identical to that described for Aims 1 and 2 except that the high density stimulating electrodes will be placed in a cap specifically designed by the manufacture rather than the 128 channel EEG recording cap (as in Aims 1 & 2). Additionally, only active tDCS will be delivered.

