Patients will be asked to have a structural MRI scan. For safety reasons and prior to the MRI scan, subjects may have a training session in the MRI simulator to help habituate and train them to the MRI environment. Per the MRI Policies and Procedures, the decision of who will be acclimated in the MRI Simulator will be made by the Research Coordinators and PI on a case-by-case basis. The PI for the study will have final say in this decision. Before the MRI scan, participants will be given an explanation of the study's procedures and screened with the MRI Safety Form for metal objects and claustrophobia. Participants will also be screened with the SAFESCAN® ferromagnetic detector according to MRI Policy and Procedures. The participant will then lie supine in the scanner. Participants will wear noise-cancelling headphones for communication and view visual stimuli through a mirror attached to the imaging head coil. Participants will undergo an anatomic scan.

The method for rTMS stimulation of the TC and for establishing the motor threshold is also identical to that described for Aims 1 and 2 except that 1800 pulses are delivered rather than 900 pulses and only active stimulation at 1 Hz will be used.

tDCS preconditioning of the DLFC will be delivered immediately prior to rTMS stimulation of the TC for three days within a one week period. rTMS will be targeted over the TC as described for Aims 1 and 2. The same safety measures will be performed before and after stimulation on each day of treatment. Additionally, analogue ratings (using a 0-100 scale) of tinnitus awareness, annoyance and loudness will be obtained at baseline and before and after each treatment session. The same ratings will also be obtained via phone, text or email on day 2, day 9 and day 16 following the last treatment. The necessary length of treatment and the timing and methods used to assess tinnitus were adopted from a previous study (109033) to ensure that the data

Study Title: Regulating homeostatic plasticity and the physiological response to rTMS
PI: [name]
Institution: University of Arkansas for Medical Sciences
Support: Department of Neurobiology and Dev. Scs.

are comparable between studies.

To assess changes in cortical excitability, EEG without and with TMS will be recorded during the baseline visit and following treatment on visit four. The primary outcome measure for TMS evoked EEG and the equipment used to assess TMS evoked EEG are described next.

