Signal processing: mitigating volume conduction. The technician will process the EEG records and import artifact-free EEG data into MATLAB (The MathWorks, Natick, MA) with the use of the EEGLAB toolbox.^{21;47} After rejecting any remaining muscle artifacts, signals will be filtered as mentioned above. [name] will download the de-identified EEG data for signal analysis.

Signal processing: calculating TEPs. Knowing that TMS pulses trigger a large, early TEP component (between 0-80 ms), consisting of a positive wave between 15 and 30 ms followed by a negative wave peaking around 50 ms, with maximum amplitude in the electrode at the TMS target;^{21;24;46} analysis of the TEP signal will occur as follows: a) a region of interest (ROI) will be defined, b) the area of the early positive and negative waves triggered by the TMS pulse will be quantified for each electrode, and c) averaged across the ROIs to obtain the local mean field power (LMFP) of TEPs for the ROI. LMFP will be calculated as the square root of squared TEPs averaged across the ROI.²¹ These analyses will be performed for each subject individually.

Risks and Benefits

Potential Risks

Risks Associated with TMS

A variety of potential risks of TMS have been identified during the last several decades. Procedures for minimizing these risks have been established³³. The following risks have been identified:

Likely: Subjects may feel anxious about participation. This typically abates after the first one or two sessions. Subjects may experience minor discomfort associated with scalp muscle twitching. Subjects typically tolerate the discomfort better as the session progress. The coil position can be adjusted if pain occurs and stimulus intensity is reduced if pain persists.

Less likely: Head and neck pain related to stimulation of underlying muscle and nerves occurs in approximately 10% of subjects. The incidence and severity is a function of stimulus site and intensity but is most common over fronto-temporal regions. The symptoms are typically limited to the time of stimulation and can be treated with minor over-the-counter analgesics if necessary.

Rare: The following have rarely been identified:

1. **Seizures:** Seizure induction represents the most serious known risk of TMS³³. Seizures have been reported more frequently in subjects with brain lesions (e.g., stroke) but have rarely been reported in subjects with no history of seizures or

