Aim 3 is being conducted as an open label feasibility study. The data may be used to derive power estimates for future studies. Subjects in this study will have completed sham and active 1 Hz rTMS treatments for tinnitus in a previous study (109033). The length of treatment, time of assessments and ratings of tinnitus used for Aim 3 are based on the previous study (109033). Therefore, we will compare change scores from baseline derived for the ratings of tinnitus in Aim 3 to changes scores from baseline derived from the sham and active 1Hz rTMS treatments in study 109033. HLMs will be used to compare mean scores for each treatment condition to provide an estimate of effect size which can be used for power calculations.

To examine change in cortical excitability following treatment, the LMFP of TEPs derived for regioins of the DLFC and temporal cortex will be compared before and after treatment using paired t-tests.

Ethical Considerations

This study will be conducted in accordance with all applicable government regulations and University of Arkansas for Medical Sciences research policies and procedures. This protocol and any amendments will be submitted and approved by the UAMS Institutional Review Board (IRB) to conduct the study.

The formal consent of each subject, using the IRB-approved consent form, will be obtained before that subject is submitted to any study procedure. All subjects for this study will be provided a consent form describing this study and providing sufficient information in language suitable for subjects to make an informed decision about their participation in this study. The person obtaining consent will thoroughly explain each element of the document and outline the risks and benefits, alternate treatment(s), and

Study Title: Regulating homeostatic plasticity and the physiological response to rTMS
PI: [name]
Institution: University of Arkansas for Medical Sciences
Support: Department of Neurobiology and Dev. Scs.

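### Aim 3 does not state that EEG processors are masked to time point, and the blind described for Aims 1 & 2 would not mask it in an uncontrolled pre-post comparison

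*Combined protocol and SAP*

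**What the plan says.** **Design and test.** The analysis text states that "Aim 3 is being conducted as an open label feasibility study". Enrolment is limited as follows: "Up to ten subjects with tinnitus who participated in a previous rTMS study". Each subject gives two recordings: "EEG without and with TMS will be recorded during the baseline visit and following treatment on visit four". The LMFP from the DLFC and the "temporal cortex will be compared before and after treatment using paired t-tests".

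**Blinding.** One sentence blinds the people who handle the EEG: "Persons who process EEG data for analysis and the biostatistician will be kept blind to condition using session codes". It stands under Aims 1 & 2, in the paragraph that opens "Methods for active and sham rTMS and study blinding". The Aim 3 methods that follow carry over the tDCS method, the rTMS method, motor threshold, targeting and safety measures. They do not mention blinding of processing. For tDCS they say: "Additionally, only active tDCS will be delivered". For rTMS they likewise allow only active 1 Hz stimulation.

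**Processing.** The shared signal-processing section says: "The technician will process the EEG records and import artifact-free EEG data into MATLAB". Remaining muscle artifacts are then rejected and an ROI is defined. No rejection threshold is given. The data passed on for signal analysis are described as de-identified, which concerns personal identity and not visit.

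**Codes.** The section on protection against loss of confidentiality builds the database code from the subject's number and the order in which testing took place.

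**The concern.** Open-label treatment does not prevent masked handling of the outcome. EEG cleaning happens after recording, so the person doing it need not know which record came first. If that person does know, and no numerical rejection rule is fixed, the two records of a pair may be cleaned differently.

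The Aim 3 EEG comparison is the part of the study least able to absorb this. In Aims 1 & 2 the outcome is a difference between sham and active rTMS, so a cleaning habit common to all sessions tends to cancel. In Aim 3 there is nothing to cancel against. The protocol also has a directional hypothesis of LTD, so a spurious fall in LMFP would look like the predicted effect.

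**Working it through.** **1. Would the existing blind mask the Aim 3 contrast?**

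| Feature | Aims 1 & 2 | Aim 3 |
|---|---|---|
| Conditions | three sham/active combinations, order randomized | one active regimen |
| Contrast of interest | sham against active | baseline against visit four |
| What a blind to condition hides | the contrast | nothing |
| What testing order reveals | not the condition | pre or post |

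So even if the blinding sentence is read as applying to every aim, it would not mask the Aim 3 contrast. A code that carries testing order would show it. The documents do not say whether the session codes and the database codes are the same.

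**2. How a cleaning difference enters the estimate.** For each subject,

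observed change = true change + (cleaning error, post − cleaning error, pre).

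The paired t-test averages this quantity. With no control arm, the mean of the bracket goes in full into the estimated change. LMFP is built from squared values, so retained artifact does not average to zero. The direction of any net effect cannot be derived from the documents.

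**3. Illustration of size.** The plan gives no power, alpha or sidedness for this test, so there is no stated figure to reproduce. Assumptions: two-sided alpha 0.05, true change zero, and a mean cleaning shift of δ SDs of the paired difference. The rejection probability is

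P(|T′| > t(0.975, n−1)), where T′ is noncentral t with n−1 df and noncentrality δ√n.

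For n = 10 the noncentrality is 0.2 × √10 = 0.632, 0.3 × √10 = 0.949 and 0.5 × √10 = 1.581.

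| δ (assumed) | n = 10 | n = 8 | n = 6 |
|---|---|---|---|
| 0 | 5.0% | 5.0% | 5.0% |
| 0.1 | 5.9% | 5.7% | 5.5% |
| 0.2 | 8.8% | 7.8% | 6.9% |
| 0.3 | 13.6% | 11.4% | 9.3% |
| 0.5 | 29.3% | 23.2% | 17.1% |

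The figures are per test, and there is one test for each region. Ten is the enrolment maximum; with fewer subjects the inflation is smaller. If masking brings a label-driven shift to zero, the rate returns to 5.0%.

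**The case against.** **Silence is not exclusion.** No sentence says that Aim 3 is outside the blind, the paragraph title refers to study blinding in general, and the signal-processing text serves all aims. This stands. A reader might infer that the protocol leaves Aim 3 processors unblinded by design; the documents do not say so. What they support is that masking of time point is not stated and that the blind as worded would not provide it.

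**No bias is shown.** Nothing in the documents says that artifact rejection is a matter of discretion, or that knowing the visit would push LMFP one way. The later steps are largely computational. This also stands: the point is that bias is possible. The percentages show what an assumed shift would do. They are not evidence that one occurs.

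**Consequences are limited.** Aim 3 is an uncontrolled feasibility study, and masked cleaning would leave time, session and regression effects in place. LMFP is named primary for Aims 1 & 2, although the Aim 3 design text says it shares those endpoints. A reader might infer that a biased LMFP change would feed planned power calculations. The text says only that Aim 3 data may be used that way, and the effect size it ties to power comes from models of the tinnitus ratings. These limits lower the weight of the point. They do not remove it, because LMFP change is still formally tested.

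**The remedy is not free.** It is tempting to say that the existing coding procedure can simply be extended at no cost. It cannot: that procedure masks condition, so Aim 3 needs a different code.

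**Conclusion.** The point holds in limited form. Followed as written, the plan does not provide for time point to be hidden during artifact rejection in Aim 3, and the comparison has no control group to absorb a difference in cleaning. This rests on three readings of the text: the blind is to condition, Aim 3 has a single regimen, and the described code includes testing order.

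The size of any bias is unknown. About 9%, 14% and 29% are illustrative rates at assumed shifts of 0.2, 0.3 and 0.5 SD, for a two-sided 5% test with the maximum of 10 subjects. It is a cheap improvement worth making. It does not show that the Aim 3 result would be wrong, and it does not bear on the sham-active contrasts of Aims 1 & 2.

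**What to change.** Add to the Aim 3 methods:

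- After visit 4, existing study staff who do not process that subject's records, or an automated routine, give both recordings random codes that omit date, visit and testing order. These replace the database code for this step.
- Artifact-rejection and ROI rules are fixed before processing starts.
- The two recordings of a pair are processed in random order under those rules.
- Time point is unmasked only after LMFP values are locked.

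**Cost.** A small recoding step, and processing of the baseline record waits until visit 4. No new subjects, visits or procedures are needed, and treatment is unchanged. Masking may be incomplete: a technician who attended the sessions may still recognise a record, and the documents do not say whether the technician who sets up sessions also processes the EEG. The report should still describe the LMFP change as an uncontrolled pre-post difference.
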